3.4 Criteria for Withdrawal

The subjects are allowed to spontaneously discontinue participation in this study at any time. The investigator may discontinue participation of a subject in this study at any time as per the subject's decision. However, a subject who are terminated early for showing a sufficient level of efficacy of the investigational product will not be considered as a withdrawal. If a subject is withdrawn from the study, the study results obtained from the discontinued/withdrawal case until the time point of discontinuation/withdrawal may be reviewed for evaluable items at the final evaluation.

In following cases, the investigator may withdraw the subject from the study.

- 1) Violation of inclusion/exclusion criteria is identified during the study.
- 2) Subjects are considered difficult to continue with the study due to adverse events as per the investigator's decision.
- 3) Subjects have received or are deemed to require medications or treatments that may affect the study results during treatment period or follow-up period.
- 4) Voluntary consent withdrawal by the subject or subject's legally acceptable representatives.
- 5) Subjects cannot not cooperate with the investigator.
- 6) Lost to follow-up.
- 7) The investigator decides to withdraw subjects.
- 8) Subject is pregnant during the study

If a subject determines to discontinue his/her participation and withdrawn from the study prior to completion, procedures scheduled for the Withdrawal visit should be performed. The procedure for the Withdrawal visit will be conducted within 2 weeks after the withdrawal decision is made. At the Withdrawal visit, the unused IPs or empty packaging will be returned, and the subject diary will be collected.

If the patient refused to visit, the vital sign, physical examination and lab test can be exclude. However, assessment of Gastroesophageal Reflux Disease Questionnaire (GERD-Q) and quality of life questionnaire (GERD-HRQL) must be performed at least by telephone call by the investigator, and all document should be written on the EMR by the investigator.s. To prevent any missing AEs that the investigator is not aware of, all kinds of methods must be employed to directly contact the subjects who refuse to visit such as phone call, letter, or personal visit. Any withdrawn subject cannot participate in the same study again.

4 Description of Study Design

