8.4 Efficacy Assessment

8.4.1 Efficacy Endpoints

8.4.1.1 Primary Efficacy Endpoint

Proportions of subjects with symptoms relief at week 4 measured by GERD-Q Score <8

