9.1 Analysis Sets

Per Protocol Set (PPS)

The PPS will include the subjects in the FAS who complete the study without any major protocol deviation. Major protocol deviations include 'violation of the inclusion and exclusion criteria', 'administration of prohibited concomitant medications during the study', etc. (see Section "13.5 Protocol Deviations"), and the subjects with other major deviations will be determined at the case report adjudication meeting prior to disclosure of randomization codes.

Full Analysis Set (FAS)

The FAS will include the subjects who receive the IP at least once after randomization and who have at least one efficacy assessment result. The subjects who violate the inclusion/exclusion criteria will be excluded from the FAS.

For the efficacy analysis, they will be included in the randomized treatment group regardless of the actual IP taken.

Safety Set

The safety set will include all the subjects who receive the IP at least once after randomization. The subjects who are enrolled in the study but withdrawn from the study before IP administration will be excluded from the safety set. For the safety analysis, the subjects will be analyzed according to the treatment they actually received.

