9.2 Statistical Analysis Method

9.2.1 General Principles of Result Analysis

The efficacy analysis will be conducted primarily on the PPS and FAS, and the PPS will be the primary analysis set.

In principle, all statistical analyses will use SAS® version 9.4 or higher and be performed with a two-sided test at a significance level of 5%, unless otherwise specified.

Descriptive statistics (mean, standard deviation, median, minimum, and maximum) will be calculated and provided for continuous variables, and the frequency and percentage will be provided for categorical variables.

The last observation carried forward (LOCF) method will be applied for correction of missing data of continuous endpoints among efficacy endpoints, and if the LOCF method cannot be applied, the raw data will be analyzed without correcting the missing data. However, the quality-of-life score (GERD-HRQL) will be analyzed using the raw data without applying the LOCF. For survival analysis, censoring will be utilized. When applying the LOCF, if the value immediately before the missing value is the baseline value, it will not be replaced.

The missing values of efficacy endpoints will be handled for both analyses on the FAS and PPS, and the safety endpoints will be analyzed with the raw data without replacing the missing values.

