9.2.3 Efficacy Endpoints

9.2.3.1 Primary Efficacy Assessment

Proportions of subjects with symptoms relief at Week 4

The proportions of subjects with symptoms relief by Week 4 and their 95% confidence intervals will be provided by group.

The proportions of subjects with symptoms relief by Week 4 will be calculated as the cumulative symptoms relief by using the results at the time of final observation including the Withdrawal visit. To compare the control group and study group, the lower bound of the 2-sided 95% confidence intervals will be obtained by using Chi Square test or Fisher's Exact test method. If this lower bound is greater than the non-inferiority margin of -0.1, the study group will be judged to be non-inferior to the control group.

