9.3 Criteria

Hypothesis: The study group (Fexuprazan 40 mg) is non-inferior to the control group (Esomeprazole 40 mg) in terms of the proportions of subjects with symptoms relief by Week 4.

To determine the noninferiority of the study group (Fexuprazan 40 mg) against the control group (Esomeprazole 40 mg), the **Chi Square test or Fisher's Exact test method** will be used. The lower limit of the 2-sided 95% confidence intervals for the difference between the study group and control group (study group minus control group) will be calculated, and if this lower limit is larger than the non-inferiority margin of -0.1, the study group will be declared non-inferior to the control group.

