9.4.2 Rationale for Determination of Sample Size

This study objective is to determine the non-inferiority of the study group (Fexuprazan 40 mg) compared to the control group (Esomeprazole 40 mg) in patients with erosive gastroesophageal reflux disease. The primary endpoint is the proportions of subjects with symptoms relief at week 4 measured by GERD-Q Score <8 , and the hypothesis is:

$$H_0: \pi_T - \pi_C \leq -0.1 \quad \text{vs.} \quad H_A: \pi_T - \pi_C > -0.1$$

π_T : Proportion of subjects with symptoms relief at week 4 (measured by GERD-Q score <8) in the study group (Fexuprazan 40 mg)

π_C : Proportion of subjects with symptoms relief at week 4 (measured by GERD-Q score <8) in the control group (Esomeprazole 40 mg)

The proportion of subjects with symptoms relief at week 4 of proton pump inhibitors (PPI) was considered to be 88.5%, and this value was set as the proportion of symptoms relief for the control group (Esomeprazole 40 mg). In this study, the proportion of symptoms relief of the study drug was assumed to be higher than control drug, therefore, 94.0% was set as the proportion of symptoms relief in the study group.

The number of subjects calculated by “Non-Inferiority Tests for the Difference Between Two Proportions” of PASS2020 with the non-inferiority margin of -0.1, the one-sided significance level of 2.5%, 80% statistical power, and 1:1 randomization allocation, was 53 per group. And considering a dropout rate of 20%, a total of 134 subjects will be enrolled in the study.

Non-Inferiority Tests for the Difference Between Two Proportions											
Numeric Results											
Test Statistic: Z-Test with Pooled Variance											
Hypotheses: H0: P1 - P2 ≤ D0 vs. H1: P1 - P2 > D0											
Target Power	Actual Power*	N1	N2	N	Ref. P2	P1 H0 P1.0	P1 H1 P1.1	NI Diff D0	Diff D1	Alpha	
0.80	0.80729	53	53	106	0.8850	0.7850	0.9400	-0.1000	0.0550	0.025	
* Power was computed using the normal approximation method.											

10 Data Management (Recording, Collection, Access, Protection, and Storage)

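### Non-inferiority is decided in completers only: the PPS leaves out subjects withdrawn before Week 4, and the FAS, which scores them by their last GERD-Q, is not required to meet the margin

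*Combined protocol and SAP*

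**What the plan says.** - **Endpoint (8.4.1.1):** "Proportions of subjects with symptoms relief at week 4 measured by GERD-Q Score <8".
- **Primary set (9.1, 9.2.1):** "The PPS will include the subjects in the FAS who complete the study without any major protocol deviation", and "the PPS will be the primary analysis set". Section 5.1 defines completion as having all protocol-specified procedures and assessments done. Efficacy is also analysed on the FAS, which needs at least one dose and at least one efficacy result and excludes eligibility violators.
- **Scoring (9.2.3.1):** relief is calculated "by using the results at the time of final observation including the Withdrawal visit". LOCF (9.2.1) is confined to continuous endpoints, so it gives no rule for this binary one.
- **Decision (9.3):** "if this lower limit is larger than the non-inferiority margin of -0.1, the study group will be declared non-inferior to the control group". The criterion names no analysis set and does not ask for agreement between sets.
- **Reasons for withdrawal (3.4):** item 2 is "Subjects are considered difficult to continue with the study due to adverse events as per the investigator's decision". Item 3 covers subjects who have received, or are judged to need, treatment that may affect the results. Prohibited medication is also a major deviation under 13.5, a second route out of the PPS.
- **GERD-Q at withdrawal:** Section 3.4 and footnote 12 of the schedule in 8.2 require it, by telephone if the visit is refused. Section 7.1 says the withdrawal procedures are not done if the subject refuses them.
- **Dropout (9.4.2):** "considering a dropout rate of 20%, a total of 134 subjects will be enrolled in the study".

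**The concern.** Withdrawal for an adverse event or for needing other treatment is related to how the assigned drug performed. Removing these subjects changes the question from relief in treated patients to relief in those who stayed to the end. If one arm loses more subjects for such reasons, its failures leave the denominator and the comparison tilts towards that arm. In a non-inferiority trial this can favour the claim.

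Two features of this plan sharpen the point. Expected dropout is 20%, twice the 10-point margin. The trial is open-label, so knowledge of treatment can influence both the decision to withdraw and the reason recorded.

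The FAS softens the problem but does not remove it. It cannot overturn the primary result, because nothing requires it to meet the margin. Its scores may also reflect time off study drug: the Withdrawal visit can fall up to 2 weeks after the decision, while GERD-Q recalls 7 days.

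**Working it through.** **1. The plan's own figure.** From 9.4.2: 94.0% versus 88.5%, margin -0.1, and "the one-sided significance level of 2.5%, 80% statistical power, and 1:1 randomization allocation, was 53 per group". With the pooled Z-test that the plan names, the mean rate is (0.94 + 0.885)/2 = 0.9125.
- Null SE = √(2 × 0.9125 × 0.0875/53) = 0.0549.
- Alternative SE = √((0.94 × 0.06 + 0.885 × 0.115)/53) = 0.0546.
- Power = Φ((0.155 - 1.96 × 0.0549)/0.0546) = 0.807, which matches the stated 0.80729.
- 53/0.8 = 66.25, rounded up to 67 per arm, or 134 in total. The plan's figures reproduce.

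**2. Can the PPS pass when the all-dosed difference is beyond the margin?** Assumptions (not in the documents): 94% relief in completers of both arms, and failure-related withdrawal of 16% (study) versus 5% (control). The chance of declaring non-inferiority is approximately Φ((Δ + 0.10)/SE - 1.96), with SE = √(pT(1-pT)/nT + pC(1-pC)/nC).

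- *PPS:* Δ = 0; nT = 67 × 0.84 = 56.3; nC = 67 × 0.95 = 63.7; SE = 0.0435. Φ(2.30 - 1.96) = **about 63%**.
- *All dosed, these withdrawals counted as not relieved:* 0.94 × 0.84 = 0.790 versus 0.94 × 0.95 = 0.893; Δ = -0.103; SE = 0.0625. Φ(-0.05 - 1.96) = **about 2%**.
- *FAS, final-observation rule:* suppose a fraction f of withdrawals in each arm has a last GERD-Q below 8 and all have a post-dose score. Relief is then 0.94(1 - w) + f·w, where w is the arm's withdrawal rate.

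| f | Study | Control | Δ | SE | Non-inferiority declared |
|---|---|---|---|---|---|
| 0.25 | 0.830 | 0.906 | -0.076 | 0.0582 | about 6% |
| 0.50 | 0.870 | 0.918 | -0.048 | 0.0531 | about 16% |
| 0.75 | 0.910 | 0.931 | -0.021 | 0.0468 | about 39% |

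**3. One data set at about the planned dropout.** Of 134 subjects, 28 withdraw, split 17 (study) and 11 (control) by assumption. Completers respond at about the planning rates. Limits are Wald 95%.

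| Analysis | Study | Control | Difference (points) | Lower limit (points) |
|---|---|---|---|---|
| PPS | 47/50 | 50/56 | +4.7 | -5.7 |
| FAS, about 25% of withdrawals <8 | 51/67 | 53/67 | -3.0 | -17.1 |
| FAS, about 50% | 55/67 | 56/67 | -1.5 | -14.3 |
| FAS, about 75% | 60/67 | 58/67 | +3.0 | -8.0 |
| All withdrawals not relieved | 47/67 | 50/67 | -4.5 | -19.6 |

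The PPS meets the margin. The FAS meets it only when most withdrawals left with a low score. With an even split of 14 and 14, the PPS lower limit is -4.9 (50/53 versus 47/53). With all withdrawals counted as failures it is -10.6 (50/67 versus 47/67).

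**The case against.** **The FAS is planned and does count failures.** A reader might infer that no planned analysis ever treats a withdrawal as not relieved, or that efficacy is examined only in completers. The documents do not support either reading. Section 9.2.1 puts efficacy on both sets, and the final-observation rule counts a last GERD-Q of 8 or more as not relieved. Because GERD-Q is required at withdrawal, the last score will normally be the withdrawal score, not the Day 7 score. This stands, and it confines the point to which set decides and to withdrawals with a low or missing last score.

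**Lack of effect is not a listed reason.** This is correct. Section 3.4 item 3 is the nearest. The FAS rule also handles lack of effect well, since a symptomatic subject will tend to score 8 or more.

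**Unequal withdrawal is assumed.** This is also correct. The Phase 2 summary in Section 1.4 reports no significant difference in adverse events among groups. Nor is every gap between PPS and all-dosed results a false claim. With withdrawal of 15% versus 5%, the all-dosed difference is 0.94 × 0.85 - 0.94 × 0.95 = -9.4 points, still inside the margin.

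**Counting withdrawal itself as failure is an estimand choice.** It brings tolerability into an endpoint defined by a symptom score, while adverse-event withdrawals are reported separately under safety. This is a sound reason not to make that analysis a condition of success. It is no reason to let a completers-only set decide alone.

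**Conclusion.** The point holds in this form. The deciding set excludes every non-completer, the FAS need not meet the margin, and no analysis counts a withdrawal for an adverse event or need of other treatment as not relieved regardless of the last score. Subjects dosed but without an efficacy result are in neither efficacy set.

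The size depends on withdrawal rates that the documents do not give by arm or by reason. If 16% versus 5% withdraw for such reasons and completers do equally well at 94%, the PPS passes about 63% of the time although the all-dosed difference is -10.3 points. The FAS would pass about 6% to 39% of the time as the share of withdrawals with a low last score goes from 25% to 75%. If withdrawals are few and balanced, the effect on the verdict is small. Nothing in the documents shows that fexuprazan will lose more subjects than esomeprazole. The weakness is that the plan would not be protected if it did.

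**What to change.** 1. In 9.2.1, 9.2.3.1 and 9.3, declare non-inferiority only if the lower 95% limit exceeds -0.1 in both the PPS and the FAS, with the FAS scored by the final-observation rule.
2. Pre-specify a sensitivity analysis in all randomised subjects who took at least one dose. A subject who leaves before the Week 4 GERD-Q because of an adverse event or need of other treatment, or who has no post-dose GERD-Q, counts as not relieved. Report it beside the PPS and FAS and discuss any disagreement. The withdrawal reason must be on the case report form.
3. Reconcile 7.1, under which withdrawal procedures may be refused, with 3.4 and footnote 12 of 8.2, which require GERD-Q.

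**Cost.** Protocol wording, one extra analysis and a stricter success rule. The power of passing both sets cannot exceed that of the FAS alone. At the planning rates in completers, with 67 per arm and 5%, 10% or 20% withdrawing in each arm, FAS power is about 81%, 74% or 60% if half of the withdrawals have a last score below 8. Relief is 0.94(1 - w) + 0.5w versus 0.885(1 - w) + 0.5w, put into the formula above.

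The sensitivity analysis should not be a condition of success. Its power at the same rates would be about 74%, 62% or 47% if all those withdrawals count as not relieved. At 20%, for example, relief is 75.2% versus 70.8%, SE = 0.0766, and Φ(0.144/0.0766 - 1.96) = 0.47.

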9.2 Statistical Analysis Method

9.2.1 General Principles of Result Analysis

The efficacy analysis will be conducted primarily on the PPS and FAS, and the PPS will be the primary analysis set.

In principle, all statistical analyses will use SAS® version 9.4 or higher and be performed with a two-sided test at a significance level of 5%, unless otherwise specified.

Descriptive statistics (mean, standard deviation, median, minimum, and maximum) will be calculated and provided for continuous variables, and the frequency and percentage will be provided for categorical variables.

The last observation carried forward (LOCF) method will be applied for correction of missing data of continuous endpoints among efficacy endpoints, and if the LOCF method cannot be applied, the raw data will be analyzed without correcting the missing data. However, the quality-of-life score (GERD-HRQL) will be analyzed using the raw data without applying the LOCF. For survival analysis, censoring will be utilized. When applying the LOCF, if the value immediately before the missing value is the baseline value, it will not be replaced.

The missing values of efficacy endpoints will be handled for both analyses on the FAS and PPS, and the safety endpoints will be analyzed with the raw data without replacing the missing values.

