When the results were analyzed by dividing into daytime and nighttime, the percentages of daytime for 7 days were not significantly different between the Fexuprazan dose groups and the Esomeprazole 40 mg group. However, Fexuprazan 40 mg showed a statistically significant difference in nighttime heartburn and heartburn + acid regurgitation compared to the control group. Therefore, it is considered that the difference in the symptom improvement resulted from acid secretion inhibitory effects sustained until the nighttime with Fexuprazan 40 mg once daily dosing. Also, no significant difference was seen from the daytime results for 8 weeks compared to the Esomeprazole 40 mg group, except for heartburn symptom. However, the Fexuprazan 40 mg showed statistically significant difference in all nighttime symptoms (heartburn, acid regurgitation, heartburn + acid regurgitation) for 8 weeks compared to the Esomeprazole 40 mg. Therefore, it can be said that Fexuprazan 40 mg significantly improves the symptoms during the treatment period because it has a rapid onset of action compared to the control group and its acid secretion inhibitory effects last until the nighttime.

With this study, it is intended to develop an acid pump antagonist that can address the unmet medical needs of PPIs which are slow onset of action and nocturnal acid rebound. In the phase 2 study, the assessment of primary efficacy endpoint showed that all Fexuprazan groups were non-inferior to the control group and did not show difference among the dose groups, but it is expected that Fexuprazan 40 mg and higher dose would show difference in symptom improvement. Therefore, the phase 3 dose was set at Fexuprazan 40 mg to confirm the efficacy and safety in patients with erosive gastroesophageal reflux disease.

2 Study Objective

This study is to evaluate symptom relief after using Fexuprazan 40 mg compared to Esomeprazole 40 mg for patient with Gastroesophageal Reflux Disease (GERD).

3 Study Population

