7.1 Overall Study Methodology

Screening Period

Subjects will provide written informed consent to participate in the study and then undergo any screening. Subjects who meet all the inclusion criteria and none of the exclusion criteria based on the screening test results will be included into the study.

Treatment Period

The subject will receive the IP consumed once daily for 1 week at Visit 2 (Day 0). Subjects will have a site visit 1 week after IP administration and prescribed the IP for another 3 weeks at Visit 3 (Day 7 ± 3 days). Subjects will visit the study at Visit 4 (Day 28 ± 5 days) to determine healing status by Gastroesophageal Reflux Questionnaires (GERD-Q).

Subjects who have not been healed at Visit 4 (Day 28 ± 5 days) will have an additional IP administration period for 4 weeks and then visit the study site at Visit 5 (Day 56 ± 5 days) to determine healing status.

If, a subject withdrawn during the treatment period will visit the study site within 2 weeks from the withdrawal decision and undergo the Withdrawal visit procedures. However, they will not be conducted if the subject refuses them.

Follow up Period

Subjects will have a Safety F/U visit within 2 weeks (± 5 days) from the day when healing is confirmed. (However, this visit will be carried out by a telephone visit. If necessary, additional examination and treatment may be performed according to the investigator's judgment.)

[figure not shown]

Figure 2. Study Schematic

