8.3.3 Questionnaire assessment

- Gastroesophageal Reflux Disease Questionnaires (GERD-Q) (See Appendix 3)
 - The subject will complete the GERD-Q at the screening visit (Visit 1) and Visit 2. The test results from Visit 1 will be used as the basis to determine eligibility for inclusion/exclusion.
 - The subjects who meet the inclusion criteria will complete the GERD-Q at Visit 3, Visit 4, and Visit 5.
- Quality of Life assessment (GERD-Health Related Quality of Life, GERD-HRQL) (See Appendix 4)
 - The subjects who meet the inclusion criteria will complete the GERD-HRQL questionnaire at Visit 2, Visit 3, Visit 4 and Visit 5.^[19, 20, 21]

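### LOCF fills a missing Week-4 GERD-Q frequency with a Day-7 or withdrawal value and analyses it as observed; this can bias a secondary comparison, in a direction the documents do not settle

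*Combined protocol and SAP*

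**What the plan says.** Section 9.2.1 sets the general rule: "The last observation carried forward (LOCF) method will be applied for correction of missing data of continuous endpoints among efficacy endpoints". It applies to both the FAS and the PPS. There are two exceptions. For quality of life, "the quality-of-life score (GERD-HRQL) will be analyzed using the raw data without applying the LOCF". For baseline, "if the value immediately before the missing value is the baseline value, it will not be replaced". The section names no sensitivity analysis for missing data.

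Section 8.3.3 fixes the post-baseline schedule: "The subjects who meet the inclusion criteria will complete the GERD-Q at Visit 3, Visit 4, and Visit 5". These are Day 7, Day 28 and Day 56, and Day 56 applies only to subjects in Treatment 2.

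For subjects who leave early and refuse a visit, section 3.4 says that "assessment of Gastroesophageal Reflux Disease Questionnaire (GERD-Q) and quality of life questionnaire (GERD-HRQL) must be performed at least by telephone call by the investigator". Section 7.1 says of the withdrawal procedures: "However, they will not be conducted if the subject refuses them".

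The binary primary endpoint has its own rule in section 9.2.3.1: "cumulative symptoms relief by using the results at the time of final observation including the Withdrawal visit".

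Section 9.2.3.2 analyses change in GERD-Q frequency by ANCOVA with treatment and baseline. The GERD-HRQL model also includes the dominant-symptom factor.

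**The concern.** LOCF assumes that nothing changes between the last visit attended and Week 4. Here that can mean three more weeks of treatment in which symptoms are expected to improve. Section 1.6 also says of fexuprazan that "it has a rapid onset of action compared to the control group", so Day 7 is a time when the two arms may differ for a reason that need not hold at Week 4. Mixing Day-7 values into a Week-4 comparison yields a blend of two time points, and an ordinary ANCOVA on the filled-in data counts each carried value as a full Week-4 observation.

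GERD-Q and GERD-HRQL are collected at the same post-baseline visits, yet one is filled by LOCF and the other is analysed on observed data only. The plan gives no reason. At stake is the reading of the Week-4 difference in GERD-Q symptom frequency.

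**Working it through.** **The plan's own figure.** The documents give no figure for the LOCF-handled endpoints. The nearest is the sample size in section 9.4.2, which supplies the 20% dropout used below. With rates 0.885 and 0.940, margin 0.10 and pooled variance:
- pooled rate = (0.885 + 0.940)/2 = 0.9125
- null SE = √(2 × 0.9125 × 0.0875/53) = 0.0549
- alternative SE = √((0.885 × 0.115 + 0.940 × 0.060)/53) = 0.0546
- power = Φ((0.155 − 1.96 × 0.0549)/0.0546) = 0.807

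This matches the printed 0.80729. Then 53/0.8 = 66.25, rounded up to 67 per group, or 134 in total. The sample size reproduces, and LOCF plays no part in it.

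**What is carried to Week 4.** Baseline is barred. The only scheduled post-baseline GERD-Q before Visit 4 is Visit 3 (Day 7). So the carried value is Day 7, or a withdrawal GERD-Q where one exists.

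**Shift with equal carrying.** Let f be the share carried in each arm, D7 the Day-7 difference and D4 the true Week-4 difference, both fexuprazan minus esomeprazole. Assume that leavers and stayers share the same mean differences.
- LOCF estimate = (1 − f) × D4 + f × D7
- Bias = f × (D7 − D4)

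**Inputs.** There are no GERD-Q frequency means or SDs in the documents. As a proxy only, section 1.4 gives phase 2 symptom-free days from the diary, in erosive disease:
- first 7 days: 43.98% − 28.27% = 15.71 points
- 8 weeks: 59.41% − 42.88% = 16.53 points

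The share f is assumed at 5%, 10% and 20%. The last equals the whole planned dropout and is an upper case.

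| Assumed D4 | f = 5% | f = 10% | f = 20% |
|---|---|---|---|
| 0 | +0.79 | +1.57 | +3.14 |
| 5 | +0.54 | +1.07 | +2.14 |
| 10 | +0.29 | +0.57 | +1.14 |
| 16.53 (phase 2, 8 weeks) | −0.04 | −0.08 | −0.16 |

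**Does the early gap narrow in phase 2?** Removing week 1 from the 8-week figure, and assuming full follow-up: (56 × 16.53 − 7 × 15.71)/49 = (925.68 − 109.97)/49 = 16.65 points for days 8 to 56. It does not narrow.

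**Unequal carrying.** Take the phase 2 levels, with 8 weeks standing in for Week 4 (true difference 16.53).
- 10% carried on fexuprazan, 20% on control: (0.9 × 59.41 + 0.1 × 43.98) − (0.8 × 42.88 + 0.2 × 28.27) = 57.87 − 39.96 = 17.91, a bias of about +1.4.
- The reverse: (0.8 × 59.41 + 0.2 × 43.98) − (0.9 × 42.88 + 0.1 × 28.27) = 56.32 − 41.42 = 14.90, a bias of about −1.6.

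**Precision.** If carried values have a similar variance and hold no information about Week 4, the standard error is too small by the factor √(1 − f). At f = 20%, √0.8 = 0.894, or about 11% too small. This too is an upper case, since a Day-7 value does hold some information.

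**The case against.** The strongest reply is that little is carried where it matters most. The PPS is the primary analysis set and holds subjects who complete the study without a major deviation, so most gaps fall outside it. A withdrawal GERD-Q is required, by telephone if necessary, and would normally replace Day 7 as the last observation. GERD-HRQL is exempt and the primary endpoint has its own rule. All of this stands, and it limits the point mainly to GERD-Q frequency in the FAS. It does not remove it: section 7.1 lets the subject refuse withdrawal procedures, section 3.4 lists loss to follow-up, and a withdrawal value taken soon after Day 7 has the same timing problem.

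A reader might infer that LOCF builds in an advantage for fexuprazan of about 3.1 points (0.20 × 15.71). The documents do not support that. The figure needs the arms to be equal at Week 4, whereas the phase 2 gap was no smaller over 8 weeks than over the first 7 days. It treats the entire dropout allowance as carried Day-7 values. It also borrows a period average of a diary measure in erosive disease, not a GERD-Q visit score. Equally, those period averages do not rule out narrowing on GERD-Q.

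One may also object that GERD-Q symptom items are 0–3 ordinal scores, a rough fit for a normal repeated-measures model. True, but the planned ANCOVA treats them as continuous already, so the change adds no new weakness there.

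**Conclusion.** The point holds as a weakness of method, not as a demonstrated bias. For GERD-Q symptom frequency, LOCF puts Day-7 or withdrawal values into the Week-4 comparison as if observed at Week 4, with no sensitivity analysis to show whether this matters. The shift is f × (D7 − D4) under equal carrying. It favours the faster-acting drug only if its early advantage narrows by Week 4, and unequal carrying can move it either way. Precision is overstated in any case.

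The size cannot be computed, because the documents give no GERD-Q frequency data. The tabulated values only illustrate the mechanism, on a proxy endpoint with assumed shares. One secondary endpoint is clearly affected, mainly in the FAS. How LOCF would act on diary symptom-free days is not described, so no claim is made there. The primary non-inferiority comparison and the sample size do not change.

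**What to change.** In sections 9.2.1 and 9.2.3.2, replace LOCF for GERD-Q frequency with a mixed model for repeated measures on the observed Day-7 and Week-4 values: treatment, visit, treatment-by-visit interaction and baseline, with unstructured covariance. Report the Week-4 contrast from it. Use the same model for GERD-HRQL, keeping its dominant-symptom covariate, so that both questionnaires are handled alike. A subject with only a Day-7 value still contributes, without the assumption of no later change. State to which visit, if any, a withdrawal value is assigned.

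Keep LOCF as a sensitivity analysis. Report Week 8 descriptively, since it is measured only in subjects who enter Treatment 2.

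The cost is SAP wording and a little more programming, with no change to sample size or visits. The downside is reliance on a missing-at-random assumption, which the SAP should state.
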